**Table 1 Schedule of Activities**

Clinical Trial Period	Screening	Treatment						Follow-Up
Visit Number	-	V 1	V 2	V 3	V 4	V 5 / EOT	Remote Visits	V 6 / EoS
Week & Window	W -4 to W 0	W 1 Day 1	W 2 ± 3 Days	W 4 ± 3 Days	W 8 ± 7 Days	W 12 ± 7 Days	V3, V4 and V6 can be performed remotely	W 14 ± 3 Days
Informed Consent 	X							
Demographics/Medical History	X	-						
Inclusion/Exclusion criteria	X							
Serum/Urine Pregnancy Test	X	X	X	X	X	X		X
Physical Examination 	X	X	X	X	X	X		X
Vital signs 	X	X	X	X	X	X		X
Clinical Laboratory Tests 	X	X	X	X	X	X		X
PK Blood Sampling 		X	X	X	X	X		
Spirometry 	X	X 	X 	X 	X 	X 		
Randomization		X						
SF-36		X	X	X	X	X	X 	
CGI Questionnaire		X	X	X	X	X		
Investigator's Tolerability Assessment				X		X		
Local IMP Tolerability		X	X	X	X	X		
IMP Administration		Twice daily administration					X	
Concomitant Medication	X	X	X	X	X	X	X	X
Adverse Events	Permanent assessment throughout the complete clinical trial period							
Drug Accountability/IMP availability check			X	X	X	X	X	

 Conduct prior to any screening activities.

 Including body weight and height (at Screening visit only), cardiovascular, respiratory, nervous, gastrointestinal, hepatic, renal, dermatological, musculoskeletal, extremities, eyes, ears, nose, throat, and lymphatic.

 Including systolic and diastolic blood pressure (sitting, after minimum 5 minutes of rest), pulse rate (sitting, after min. 5 minutes of rest), body temperature (the same method should be used for each patient and throughout the clinical trial), and respiratory rate.

 According to Section 12.1.6. of the protocol

 Day 1 blood samples at pre-dose, directly after end of inhalation, 15, 30, 45 min (+/- 5 minutes), and 1, 1.5, 2, 4 h (+/- 15 minutes), after end of inhalation. Other visits are a trough (pre-dose – 15 min before inhalation) sample only.

 According to [Section 12.1.1.](#) of the protocol

 Spirometry results at screening visit are required to confirm BOS diagnosis. The assessment is allowed to be performed +/- 2 days from screening visit date (but has to be performed after informed consent was given by the patient).

 applicable for remote Visits 3 and 4 only

## 8.2 Randomization and Stratification

At the Baseline visit (V1), after all inclusion and exclusion criteria have been fully evaluated, eligible patients will be assigned to one of the three treatment groups at a ratio of 1:1:1 by means of block randomization.

No stratification will be performed.

## 8.3 Primary Endpoints

- Investigational medicinal product (IMP) tolerability and safety during the first 4 weeks of treatment. IMP tolerability will be assessed using the following outcomes:
  - Local Tolerability:
    - Cough
    - Wheezing
    - Bronchospasm
    - Throat irritation
    - Change in FEV1
  - Overall Tolerability:
    - Clinical Global Impressions (CGI) scale
    - Investigator's tolerability assessment
  - Safety:
    - Adverse events (AEs)
    - Serious adverse events (SAEs)
    - Clinical laboratory values
    - Vital signs
    - Physical examination

## 8.4 Secondary Endpoints

- IMP tolerability and safety during the first 12 weeks of treatment (using the outcomes listed in Section 8.3)
- CsA PK, using the following parameters:
  - Week 0, at pre-dose; directly after end of inhalation; 15, 30, and 45 minutes, and 1, 1.5, 2, and 4 hours after end of inhalation: Cmax, tmax, AUC0-4h
- Whole blood trough levels parameter (Cyclosporine A Concentration) at week 2, 4, 8, and 12

## 8.5 Exploratory Endpoints

The following measures of treatment efficacy will be analyzed as exploratory assessments:

- FEV1 % predicted, FEV1/FVC at randomization compared to Week 2, Week 4, Week 8, and Week 12
- SF-36 Quality of Life Questionnaire at Week 2, Week 4, Week 8, and Week 12
- Changes in the dose of corticosteroids and immunosuppressive therapy administered throughout trial duration

For efficacy assessments determined at post-baseline visits, measured values as well as change from baseline will be analyzed.

## 8.6 Safety Endpoints

See Sections 8.3 and 8.4.

# 9 STATISTICAL CONSIDERATIONS

## 9.1 General Considerations and Descriptive Statistics

Analyses and outputs will be produced using SAS® software PPD, version 9.4 or later, or other suitable, commercially or publicly available statistical software, in a secure and validated environment. All tables, figures and data listings to be included in the report will be independently checked for consistency and integrity.

The data recorded in the eCRF will be summarized as appropriate, per treatment group and for the applicable total analysis population, using the following descriptive measures:

- All continuous assessments will be summarized using descriptive statistics (i.e., n, mean, standard deviation, median, Q1, Q3, minimum, and maximum).
- All categorical assessments will be summarized by using frequency counts and percentages.
- Discrete ordinal or higher-level data will be summarized as continuous data, but a tabulation of categories may also be included, depending on the number of categories.
- “Missing” category should be added for a categorical variable if there is at least one subject with missing data for that categorical variable unless the following evaluation requires otherwise.

For all measures analyzed, tabulations comparing the treatment groups will be prepared. For outcomes measured more than once, the analyses will include tabulations of the measured values

---

by visit, as well as change from baseline. Where provided, all confidence intervals will be two-sided 95% intervals.

All data recorded in the eCRF will be listed in subject data listings.

### **9.1.1 Imputation of Missing data**

There will be no imputation of data for efficacy analysis. All data will be analyzed as they appear in the database. Missing data will be displayed in subject data listings and will be declared in tables as appropriate.

The following imputation rules will apply only for AE data:

- Imputed data should be flagged and properly footnoted as “imputed”.
- AEs with unknown onset date/time will be counted as treatment emergent AEs (TEAEs).
- AEs/TEAEs with unknown end date/time will be counted as an ongoing AEs/TEAEs, unless ongoing was ticked on the CRF.
- TEAEs will be considered potentially IMP related if the investigator’s rating of the causal relationship is anything other than ‘not related’ or missing.
- If for the calculation of a time period the full date format ddmmmyyyy is needed, missing entries will be imputed as follows:
  - Missing day in start date of a time period is imputed by the first day of the month;
  - Missing day in stop date of a time period is imputed by the last day of the month;
  - Missing month in start date of a time period is imputed by January of the year;
  - Missing month in stop date of a time period is imputed by December of the year;
  - Missing year is not imputed.

## **9.2 Sample Size Considerations**

This is a Phase IIa study in a rare indication, with very limited availability of eligible patients and a purely descriptive statistical concept. Accordingly, the sample size for the study was established based on considerations of feasibility rather than on power calculations.

A total of 24 patients (3 arms with 8 patients in each) are planned to be randomized.

### **9.2.1 Interim Analysis for Sample Size Re-estimation**

Not applicable.

## **9.3 Type I Error Considerations**

Not applicable.

## **9.4 Data Monitoring Committee and Confidentiality of Results**

An independent Data Monitoring Committee (DMC) will be established to monitor the safety of the IMP throughout the conduct of the study. The statistical analysis to be prepared for the meetings of the DMC are described in a separate SAP.

# **10 DEFINITIONS**

## **10.1 Protocol Deviations**

According to the Protocol Deviation Management Plan, PDs are classified as either Important PDs (IPDs) or Non-important PDs (N-IPDs). IPDs are a subset of PDs that may significantly impact the completeness, accuracy, and/or reliability of the trial data or that may significantly affect a subject's rights, safety, or well-being. Additionally, PD related to Covid-19 will be classified.

IPDs for which a significant influence on the assessment of treatment efficacy cannot be excluded will lead to the exclusion of a subject from an efficacy analysis data set (see Section 10.2 below). The impact of PDs on the efficacy endpoint results will be investigated by assessing the robustness of the efficacy results and conclusions to the choice of analysis population, both including and excluding data potentially affected by such PDs (see Sections 10.2.2 and 10.2.3 below).

The relevant PDs have to be defined by a systematic data review prior to database closure. For this purpose, PDs that occurred during the study such as deviations of inclusion/exclusion criteria or forbidden concomitant medications or subject non-compliance will be assessed as 'important' or 'non-important' depending on their potential to interfere with the objectives of the study. Listings will be prepared to show the eligibility of all subjects. Comprehensive justification for the classification of a protocol deviation as "important" will be given in the integrated clinical study report.

Important protocol deviations and the assessment of analysis sets will be defined during the data review before data base closure. All definitions given in the Minutes of the Final Data Review will be taken into account in the analysis.

The list of protocol deviations will be reviewed by the sponsor and finalized before locking the database. The sponsor will identify important PDs which will lead to exclusion of subjects from PP population. Important PDs leading to the exclusion of patients from the analyses sets will be flagged in the protocol deviation listing.

## 10.2 Analysis Data Sets

The term ‘analysis data set’ is used to define the set of patients to be included in a class of analyses. The analysis data set is described in terms of the specific criteria for patient inclusion.

Eligibility for the analysis data sets will be determined in a Blind Data Review Meeting (BDRM) held after closing the database but before unblinding the random code. To maintain the blinding of the meeting participants in this single-blind study, information on protocol deviation as well as any other subject data will be presented during the BDRM in a format that assures that the actual treatment assignment of the subjects will not be revealed.

Detailed justification for the classification of a protocol deviation as having an important influence on the assessment of treatment efficacy will be given in the BDRM minutes as well as in the integrated CSR.

### 10.2.1 Safety Analysis Set

The Safety Analysis Set (SAF) is defined as all randomized patients who have received a partial dose of IMP at least once. All data collected after baseline to the end of clinical trial participation will be included in the safety summaries. Patients will be analyzed according to the treatment they actually received.

All safety and tolerability data will be summarized and analyzed using the SAF.

### 10.2.2 Full Analysis Set

The Full Analysis Set (FAS) is defined as all randomized patients for whom a baseline and at least one post-baseline measurement of an efficacy outcome measure, i.e., for spirometry or quality of life measures (Section 8.5), is available. For spirometry measures, baseline will correspond to the assessment at randomization visit (Visit 1) prior to inhalation of IMP. Patients will be analyzed according to the treatment group to which they were randomized.

A BDRM will determine if patients should be excluded from the FAS in cases of significant protocol deviations that preclude an assessment of treatment efficacy (e.g., randomized patients not suffering from the condition under investigation). Any exclusion of patients from the FAS will require individual justification.

The primary analysis of all efficacy endpoints will be performed using the FAS.

### 10.2.3 Per Protocol Set

The Per Protocol Set (PPS) is defined as all patients included in the FAS

- who complete randomized treatment as scheduled or who are withdrawn prematurely due to lack of efficacy or lack of tolerability of the clinical trial treatment, and
- for whom no IPD leading to exclusion from PPS was identified during the data review meeting. The IPD criteria will be defined in the protocol deviation (PD) list and reviewed before database closure. The reviewed PD list will be included into the CSR.

Patients with one or more AE related to IMP will be discussed during the BDRM to decide if there is a lack of tolerability.

Patients with “AE (including SAE/Death)”, “Investigator's withdrawal of subject in the best interest of the patient” or with free text “Lack of efficacy” as primary reason for non-completion of the study will be discussed during the BDRM to decide if there is a lack of efficacy.

For selected efficacy endpoints, the PPS may be used as a sensitivity analysis to assess the impact of important protocol deviations on the results.

Patients will be analyzed according to the treatment they were randomly assigned.

## 10.3 Definitions Related to Safety Data

### 10.3.1 Treatment-emergent Adverse Events

Treatment-emergent adverse events (TEAEs) are defined as AEs with onset on or after the IMP intake or pre-existing and worsening after IMP intake.

### 10.3.2 Treatment-related Adverse Events

The Investigator will assess the relationship (unrelated, possible, definite) of each AE to the investigational treatment (L-CsA (10 mg bid or 5 mg bid) plus SoC or SoC alone). Treatment-related AEs are defined as events with any causal relationship other than ‘not related’ according to the assessment of the Investigator. Patients who experience the same event multiple times will be included in the most related category for summarization.

## 10.4 Study Day and Time from Randomization

Baseline is defined to be the day of the randomization visit (visit 1, week 0). Time from baseline (days) for subsequent visits is defined to be visit date – date of randomization visit + 1.

## 11 DISPOSITION

The number of patients screened, who failed screening, randomized, treated with clinical trial treatment and completing the clinical trial (and reason for not completing) as scheduled will be presented in frequency tables by treatment group.

The number of randomized patients in each analysis population (SAF, FAS and PPS) will be summarized by treatment group. A by-patient listing of disposition will be provided.

All important protocol deviations will be presented as a frequency table by treatment group. All protocol deviations will be presented in a by-patient listing, which will include the category of the deviation, the deviation text, if it was an important protocol deviation and if the PD led to the exclusion from FAS and/or PP.

A separate listing will be provided for covid-19 related protocol deviations.

## 12 BASELINE DEMOGRAPHICS AND DISEASE CHARACTERISTICS

All baseline demographic, anthropometric, medical data will be summarized by treatment group for the SAF, FAS, and PPS analysis populations. For summary purposes, the most recent, non-missing result obtained on or prior to the baseline visit will be used.

Prior and concomitant medication will be summarized and tabulated according to the 1st and 2nd levels of the WHO ATC system. The version will be provided in Data Management related document “DM-AD-089-Study-specific Dictionary Coding Conventions and Specifications”. Non-IMP medication will be assessed as prior treatment when the start of the treatment lies before the baseline visit, and as concomitant medication for any treatment started or ongoing after baseline. The definition implies that medication started before the baseline visit but continued into the randomized treatment phase will be both prior and concomitant.

In case of incomplete information for start of non-IMP medication, the earliest possible date will be assumed for determining whether treatment is prior and/ or concomitant (e.g., ‘2019’ will be assumed to indicate ‘01-Jan-2019’). For incomplete information on treatment end, the latest possible date will be assumed unless it lies in the future (e.g., ‘09-2017’ will be assumed to indicate ‘30-Sep-2017’). Medication with an entirely missing start date will be assumed to be prior treatment. Similarly, medication with an entirely missing stop date will be assumed to be ongoing during randomized treatment.

Time from Transplantation to BOS Score 1 Diagnosis (days) will be summarized and is derived as: Date of BOS Score 1 Diagnosis – Date of Transplantation + 1.

---

By-patient listings will be provided for all baseline demographic and disease characteristics.

## 13 PRIMARY ASSESSMENTS

The primary assessments will be measures of safety and local tolerability listed in Section 8.3 and covering the first 4 weeks of treatment, defined as data collected until Visit 3. AEs will be included into this analysis if their date of onset lies on or before Visit 3 or, in case of an incomplete or missing date of onset, if they could have started on or before Visit 3 in accordance with all available information, using the procedure for incomplete data information already described in Section 12 above.

Outcomes assessed during study visits will be included into the primary analysis up until Visit 3 scheduled to be performed at Week 4 after baseline, or until the EoT visit if it was performed on or before Visit 3.

All analyses described in this chapter will be performed on the SAF.

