9.3.1 Procedures of Patient Withdrawal and IMP discontinuation

Withdrawal:

The patient is free to withdraw from the clinical trial for any reason and at any time without giving a reason for doing so and without penalty or prejudice. The Investigator is also free to terminate a patient's involvement in the clinical trial at any time if the patient's clinical condition warrants it. In case of early withdrawal, the patient will be encouraged to perform a final visit. The final visit will encompass the assessments listed under EoS Visit ([Section 13.2.5](#)).

Additionally, used and unused IMP and inhalation device will be retrieved, if applicable. Zambon SpA will be notified by the Investigator via entry in and notification by the eCRF that the patient has terminated clinical trial participation.

IMP discontinuation

The Investigator or patient is free to discontinue regular intake of IMP, if the clinical condition of the patient or other serious reasons warrant it. Reasons for discontinuation of IMP may include (but are not limited to) the following:

- Significant respiratory infection requiring therapy
- Respiratory failure from any cause
- Mechanical ventilation

If 10 or more consecutive doses of IMP are missed, regardless of reason, then IMP will be considered as discontinued and should not be resumed. If IMP inhalation is discontinued, the patient will be asked to return for clinical trial visits according to the visit schedule defined in the protocol but shall not receive IMP.

Stopping criteria are outlined in detail in [Section 8.5.1](#).

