9.3.2 Type and Timing of Data Collection for Patient Withdrawal and IMP discontinuation

All cases of patient withdrawal or discontinuation of IMP will be recorded on the applicable eCRF pages by the Investigator including date and reason.

Patients who are discontinued should have the final clinical trial visit procedures performed within 1 month after stopping IMP, if possible. For details of the procedures, please refer to [Section 13.2.5, Visit 6/End of Study](#).

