9.3.3 Replacement of Withdrawn Patients

Patients withdrawn before randomization will be regarded as screen failures. A sufficient number of patients will be screened until the pre-defined number of randomized patients has been reached. Randomized patients will not be replaced. However, patients prematurely withdrawn from treatment should be encouraged to continue to participate in the clinical trial until the scheduled end. The eligibility of prematurely withdrawn patients for the different analysis populations will be determined in a blind data review meeting with consideration of the definition of these analysis populations provided in [Section 14.1](#).

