12.1.5 Tolerability of IMP

Local tolerability findings will be recorded as AEs in the appropriate eCRF.

The patient will be observed for local tolerability findings for 1 hour after inhalation at each on-site study visit.

Local tolerability events are:

- Cough
- Wheezing
- Bronchospasm

- Throat irritation
- Change in FEV₁

In addition, these events will be solicited actively before IMP inhalation at each study visit (except EoS) by questioning the patient whether he/she has experienced any of the events in-between the study visits. If applicable, an AE report form will be completed.

Overall tolerability assessment by the investigator includes:

- CGI questionnaire ([Guy 1976](#))
- Investigator's tolerability assessments at Visit 3 and Visit 5, assessed by means of a five-point verbal rating scale with the response options 'very good', 'good', 'satisfactory', 'moderate', and 'poor'

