13.2.3 Visit 2 through Visit 5 / EoT

- Physical examination
- Vital signs
- Clinical laboratory tests
- Cyclosporine A whole blood trough levels (blood sample pre-dose)
- Urine/Serum pregnancy test
- Spirometry
- IMP Administration
- Concomitant medications/therapies
- AEs
- CGI (Items 1-3)
- SF-36 questionnaire
- Local IMP tolerability
- Drug Accountability by vial count (Visit 5 only)
- Check IMP supplies of patient

13.2.4 Visit 3 and Visit 5

- In addition to the assessments described in section 13.2.3, the clinical investigator will perform an Investigator's Tolerability Assessment assessed by means of a five-point verbal rating scale with the response options 'very good', 'good', 'satisfactory', 'moderate', and 'poor'.

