## **13.2 Analysis of Overall Tolerability**

The CGI is a 3-item observer-rated scale that measures illness severity, global improvement or change and therapeutic response. A modified version of the CGI will be used in this trial to assess “illness” instead of “mental” illness. For CGI Items 1 and 2, a table of frequencies as well as a table of summary statistics will be produced, broken down by treatment group and visit. Item 3 will only be tabulated in frequency tables. The two dimensions of the item, ‘Therapeutic effect’ and ‘Side effects’, will be tabulated separately and overall.

For all CGI Items, a score of 0 (‘Not assessed’) will be treated as missing data and will thus be excluded from the computation of summary statistics. The scale does not support the computation of a summary (total) score.

A table of frequencies will be prepared for the Investigator’s Tolerability Assessment at Visit 3.

Pairwise treatment group comparisons will be performed for CGI Items 1 and 2, for the dimensions of Item 3 assessed separately as well as for the Investigator’s Tolerability Assessment using Wilcoxon-Mann-Whitney U-tests. Comparisons for CGI between treatment groups will be provided for Visit 3 and for Visit5/EOT.

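### Overall-tolerability ratings of patients who stop IMP but stay in the trial may be made off drug or not at all, and the SAP does not separate them in the between-arm comparison

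*SAP*

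**What the plan says.** **After IMP is stopped.** Protocol 9.3.1 asks these patients to "return for clinical trial visits according to the visit schedule defined in the protocol but shall not receive IMP". Protocol 9.3.3 adds that "patients prematurely withdrawn from treatment should be encouraged to continue to participate in the clinical trial until the scheduled end". Protocol 9.3.2 says something different: "Patients who are discontinued should have the final clinical trial visit procedures performed within 1 month after stopping IMP", and refers to Visit 6/End of Study for the procedures. Protocol 13.2.5 lists those procedures, and neither the CGI nor the Investigator's Tolerability Assessment is among them.

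**When overall tolerability is rated.** Protocol 12.1.5 provides for "tolerability assessments at Visit 3 and Visit 5, assessed by means of a five-point verbal rating scale", and 13.2.4 repeats the two visits. The CGI is due at Visits 1 to 5, but at Visit 1 only Item 1 is completed (Protocol 12.1.9, 13.2.2, 13.2.3). Item 3 has a side-effects dimension (SAP 13.2).

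**How the ratings are analysed.** SAP 8.3 lists the CGI and the Investigator's Tolerability Assessment under the primary endpoints. SAP 13 says "Outcomes assessed during study visits will be included into the primary analysis up until Visit 3", or up to the EoT visit if that was held on or before Visit 3. The analysis set is the SAF, which needs only one partial dose (SAP 10.2.1). SAP 13.2 compares arms pairwise with Wilcoxon-Mann-Whitney tests and adds that "Comparisons for CGI between treatment groups will be provided for Visit 3 and for Visit5/EOT". SAP 14.1 extends the analyses to the whole treatment period as secondary. SAP 13.7 plans no sensitivity analysis for the primary endpoint, and Protocol 14.4 rules out imputation.

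**The concern.** The rating is meant to describe how well IMP was tolerated over the first 4 weeks. Neither document states the period a rating covers, requires a rating when IMP is stopped, records whether the patient was on drug when rated, or says how an off-drug rating enters the comparison. For someone who stopped because of cough or bronchospasm, a rating made weeks later may describe a patient whose side effects have gone. It would then be ranked alongside ratings of patients still inhaling.

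If the 9.3.2 route is followed, the rating is absent and the intolerant patient drops out of the comparison. Both routes can make the overall-tolerability result of an arm look better than the patients' time on drug was. Tolerability is the trial's main question, each arm has 8 patients, and a few such patients can change the picture.

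**Working it through.** **Step 1: can a rating be off drug?** Protocol 9.3.1 treats IMP as discontinued after 10 consecutive missed doses, which is 10 / 2 = 5 days at two doses a day. Visit 3 is at Week 4 ± 3 days, so 25 to 31 days after baseline. A patient who stops 5 days after baseline and attends Visit 3 has been off drug for 20 to 26 days. The Investigator's Tolerability Assessment has no scheduled time point before Visit 3, so anyone who stops earlier has no scheduled on-drug rating. CGI Item 3 is first due at Visit 2 (Week 2 ± 3 days, 11 to 17 days after baseline), which is also off drug for this patient.

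**Step 2: does the EoT clause in SAP 13 catch this?** Both documents define EoT as Visit 5 at Week 12. Patients who leave early are directed to End of Study procedures (Protocol 8.5.1, 9.3.1). No EoT visit is triggered by stopping IMP, so the clause does not clearly reach these patients.

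**Step 3: which result is primary?** Only Visit 3. Visit 5 belongs to the 12-week secondary assessment (SAP 8.4). The opening sentence of SAP 13 names only safety and local tolerability as primary, but SAP 8.3 lists overall tolerability as primary and SAP 13.2 sits in the primary chapter.

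**Step 4: possible size.** The plan has no power calculation to reproduce. Its only figure is 3 × 8 = 24, which agrees. The ratings and stopping counts below are assumptions.

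Scale: 1 = very good to 5 = poor. Placebo (n = 8): two rated 1, four rated 2, two rated 3. The measure is the probability that an active patient is rated worse than a placebo patient, ties counted half. Each active rating contributes:
- rating 1: (0 + ½ × 2) / 8 = 0.125
- rating 2: (2 + ½ × 4) / 8 = 0.50
- rating 3: (6 + ½ × 2) / 8 = 0.875
- rating 4 or 5: 8 / 8 = 1

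With 3 stoppers, the other 5 active patients are rated 1, 2, 2, 2, 3 and contribute 0.125 + 3 × 0.50 + 0.875 = 2.5.
- Stoppers *poor* for time on drug: (2.5 + 3) / 8 = 0.6875
- Stoppers *good* while off drug: (2.5 + 1.5) / 8 = 0.50
- Stoppers missing: 2.5 / 5 = 0.50

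The same calculation for other counts, with exact two-sided Wilcoxon-Mann-Whitney p in brackets:

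| Stoppers of 8 | Ratings of the others | Stoppers *poor* | Stoppers *good* off drug | Stoppers missing |
|---|---|---|---|---|
| 1 | 1,1,2,2,2,3,3 | 0.56 (0.79) | 0.50 (1.0) | 0.50 (1.0) |
| 2 | 1,2,2,2,3,3 | 0.67 (0.29) | 0.55 (0.98) | 0.56 (0.71) |
| 3 | 1,2,2,2,3 | 0.69 (0.23) | 0.50 (1.0) | 0.50 (1.0) |
| 4 | 1,2,2,3 | 0.75 (0.11) | 0.50 (1.0) | 0.50 (1.0) |
| 5 | 2,2,3 | 0.86 (0.016) | 0.55 (1.0) | 0.63 (0.66) |

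**Step 5: how likely is any such patient?** The documents give no discontinuation rate. If the chance of stopping for intolerance before Visit 3 is p, at least one of the 16 active patients stops with probability 1 − (1 − p)^16. This is 0.56, 0.81 and 0.97 for assumed p of 5%, 10% and 20%.

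**The case against.** A reader might infer that the primary analysis as a whole records intolerance as good tolerability. The documents do not support that. Up to Visit 3 the SAP also tabulates by arm TEAEs leading to treatment discontinuation, severe TEAEs and related TEAEs (SAP 13.3.1). Local tolerability events are tied to the hour after an inhalation (SAP 13.1). Intolerance stays visible there, and only the overall-tolerability component is exposed.

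Nor is a falsely good rating certain. The object rated is IMP, the investigator is not blinded (Protocol 8.3.1), and a rater who knows the patient stopped may well score the time on drug. CGI scores of 0 for not assessed are treated as missing (SAP 13.2). Unscheduled visits refer to the Protocol 13.2.3 assessments, so a CGI could be collected at the stop, though none is required.

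It is also tempting to call the bias one-sided. It probably runs towards hiding intolerance, but this is not shown. Placebo patients inhale a liposomal product and may stop too, stops may follow infection or respiratory failure, and an unblinded rater could be harsh on stoppers.

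Finally, the illustration with 3 or 4 stoppers is severe, since the protocol describes L-CsA as well tolerated in earlier trials. With one stopper the contrast is only 0.56 against 0.50, and p-values are descriptive (Protocol 14).

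All of this limits the scope and size of the point. It does not supply the missing rating period, the missing on- or off-drug flag or a rule for these patients, and it leaves 9.3.1 and 9.3.2 in conflict.

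**Conclusion.** The point holds for the overall-tolerability component: the Investigator's Tolerability Assessment and CGI Item 3 side effects, at Visit 3 as primary and at Visit 5 as secondary. Patients who permanently stop IMP but stay in the trial may be rated off drug or not rated, depending on which protocol section a site follows, and the comparison on the SAF does not distinguish them.

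The effect on the result cannot be quantified from the documents. Under the assumed ratings, 3 stoppers of 8 move the probability of a worse rating from 0.69 to 0.50 by either route, and 4 stoppers move it from 0.75 to 0.50. These figures depend on the stopping counts, on the stoppers' on-drug rating being *moderate* or *poor*, and, for the off-drug route, on a later rating of *good*. The practical harm is an overall-tolerability table that may disagree with the adverse event tables with no prespecified way to explain why.

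**What to change.** 1. **Protocol 9.3.1 and 9.3.2:** reconcile the two sections on which visits and forms apply after IMP is stopped.
2. **Protocol 13.2.4:** when IMP is permanently stopped before Visit 3 or Visit 5, complete the Investigator's Tolerability Assessment at the contact where the stop is recorded and, if that contact is on site, CGI Item 3 as well. State on the form that the rating covers the time on IMP.
3. **SAP 13.2:** use that rating in the Visit 3 or Visit 5 between-arm comparison. Flag ratings made off IMP and tabulate them separately.
4. **SAP 13.7:** add a sensitivity analysis in which stops for intolerance take the worst rank. The data review meeting already has to judge lack of tolerability for the PPS (SAP 10.2.3), so the classification can be taken from there.

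Do not carry the Visit 2 CGI forward. For an early stopper it is already off drug, and the Investigator's Tolerability Assessment has no Visit 2 rating. Leave CGI Items 1 and 2 by visit as planned, because moving their time point would mix disease course into the comparison.

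The cost is one short extra completion of existing forms per stopper, some protocol and SAP wording, and rating times that differ slightly between patients.
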